Treatment strategies	
 
Have an immunocompromised condition         (ascertained by registered diagnosis of solid         malignancy, hematologic malignancy,         rheumatologic or inflammatory disorder, other         intrinsic immune condition or immunodeficiency,         organ or stem cell transplant, or received a Covid-         19 vaccine dose equivalent of booster dose for         immunocompromised)
 
For the target trial comparing booster vs unboosted:         1) Receive a BA.1 or BA.4-5 bivalent booster         2) Do not BA.1 or BA.4-5 bivalent booster and         continue being unboosed during follow-up
 
For the target trial comparing between boosters:         1) Receive a BA.1 bivalent booster         2) Receive a BA.4-5 bivalent booster         3) Receive an original monovalent         The bivalent (or original monovalent) booster is         received as a 4th dose within the general population         (objective #1-#2, #5-#8) and as any booster (≥4th)
 
	Same as for the target trials. We define the date of booster vaccination (that is, the index date) according to the registered date of administration.
	dose for the immunocompromised population	
	(objective #4)	
Treatment assignment	Individuals are randomly assigned to a strategy at baseline in a 1:1 ratio (for immunocompromised population, conditional on number of previous doses received). Individuals will be aware of the assigned treatment strategy.	Individuals are assigned to the strategy compatible with their type of booster received; randomization is assumed conditional on matching (in a 1:1 ratio) on baseline covariates; unboosted are assigned the index data of the matched booster.
		date of the matched booster recipient.
Outcomes	Covid-19 hospitalization (ascertained by positive SARS-CoV-2 PCR test in relation to Covid-19 registered inpatient hospitalization) and Covid-19 death (ascertained by positive SARS-CoV-2 PCR test in relation to any (or Covid-19 cause-specific [in Norway]) death.	Same as for the target trials.
Follow-up	Follow-up for each individual will start at day 8 from	Same as for the target trials.
	treatment assignment (to ensure full immunisation among booster recipients) and end on day of outcome event, death, loss to follow-up, receipt of additional booster, 365 days (and 180 days for immunocompromised population) after baseline, or end of data collection, whichever occurs first.	
Causal contrast	Per-protocol	Observational analog to per-

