#### **Covariates**

For our main cohort analysis objective #1-2 and #5-8, we will take the following potential confounders into account: age (using birth cohort), sex, region of residency, calendar time of last mutual vaccine dose (i.e., either third or fourth dose depending on boosted vs unboosted- [i.e., 4 vs 3-] or between boosters- [i.e., 4 vs 4-] analyses), vaccination priority group (nursing home residents, healthcare personnel, at risk of severe Covid-19 due to comorbidities), previous SARS-CoV-2 infection and selected comorbidities. For the Covid-19 hospitalised cohort analysis (objective #3), we will also include length of hospitalisation as a covariate (as a proxy for severity of event) but not use previous SARS-CoV-2 infection history (as per eligibility criteria, all included are SARS-CoV-2 infected [as hospitalised due to this infection] and any previous SARS-CoV-2 infection is most likely not a strong confounder within the comparison). For the immunocompromised cohort analysis (objective #4), we will also include subtype of immunocompromised condition (as categorized in the 6 levels in the table above). In addition, we will assess the data distribution to help find the optimal categorization of the variables "Time since SARS-CoV-2 infection", "Time between primary course and first booster", and "Time between first and second booster". Further details of covariate definitions are provided in table below.

Variable	Country	Data source and details	Values/codes
Ago	Denmark	The Civil Registration System. Recorded birth year. Age defined as the country-specific start date minus birth year.	Categorical (for adjustment, using birth year): 5-year bins
Age	Finland	The Finnish Population Information System. Recorded birth year. Age defined as the country-specific start date minus birth year.	Binary (for stratification): ≥ 70 years</td

Variable	Country	Data source and details	Values/codes	
	Norway	Norwegian Population Register. Recorded birth year. Age defined as the country-specific start date minus birth year.		
Sweden		The Total Population Register. Recorded birth year. Age defined as the country-specific start date minus birth year.		
	Denmark	The Civil Registration System. Defined as registered sex.		
Sex	Finland	The Finnish Population Information System. Defined as registered sex.	Binary: male, female	
Jex	Norway	Norwegian Population Register. Defined as registered sex.	billary. maie, lemaie	

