## 9.7 Data analysis

#### **Procedures**

[figure not shown]
We will use a matched study design to evaluate the effectiveness of a bivalent BA.1 or BA.4-5 (or monovalent [original]) mRNA-booster vaccine (as the fourth dose) in comparison with having received three monovalent vaccine doses only (i.e., nonboosted with a fourth dose) as well as between fourth dose recipients. For the boosted vs nonboosted (i.e., 4 vs 3 dose) comparisons, individuals who have received a fourth dose will be matched on the day of vaccination with individuals who have not yet received a fourth dose. Individuals will be matched on age (5-year bins), calendar time according to when the third dose was received (monthly bins), and a propensity score including sex, region of residence, vaccination priority groups (i.e., individuals at high-risk of severe Covid-19 or healthcare workers), selected comorbidities (chronic pulmonary disease, cardiovascular conditions or diabetes, autoimmunity-related conditions, cancer, and moderate to severe renal disease), and previous history of SARS-CoV-2 infection characteristics. The day the fourth dose was administered within each matched pair will serve as the index date for both individuals. If individuals who were included as a

matched nonboosted (previously three-dose vaccinated) individual (i.e., a reference individual) received a fourth dose later than the assigned index date, they will be allowed to potentially re-enter as a fourth-dose recipient in a new matched pair on that given date. The figure below illustrates the study cohort construction.

For the between booster (i.e., 4 vs 4 dose) comparison, BA.4-5 booster and BA.1 booster recipients (as a fourth dose) will be matched on age (5-year bins), calendar time according to when the fourth dose was received (monthly bins), and a propensity score including sex, region of residence, vaccination priority groups (i.e., individuals at high-risk of severe Covid-19 or healthcare workers), selected comorbidities (chronic pulmonary disease, cardiovascular conditions or diabetes, autoimmunity-related conditions, cancer, and moderate to severe renal disease), and previous history of SARS-CoV-2

infection. The day the fourth dose was administered will serve as the index date for each respective individual. The figure below illustrates the study cohort construction.

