## Statistical analysis

We will use logistic regression to estimate the propensity score of receiving a specific booster dose given covariates as predictors. We will match (without replacements) on age, calendar time of last mutual vaccine dose (i.e., third or fourth dose), and the propensity score (with a calliper width of 0.01).

Cumulative incidences will be estimated by the Kaplan-Meier estimator, and from these we will calculate the comparative VE as 1 – risk ratio at day 365. The corresponding 95% CI will be calculated using the delta method. Country-specific estimates will be combined by random-effects meta-analyses implemented using the *mixmeta* package in R.

Comparative waning will be estimated using meta-regression.(39) First, we will estimate the VEs (in the specific comparison being evaluated) in each consecutive three-months period (day 8-90, day 91-180, 181-270, and 271-365) by stratification on time since booster vaccination. Second, the resulting estimates will be analysed using meta-regression to provide a ratio of VEs per three-month intervals as a measure of waning.

Subgroup analyses will be conducted according to sex, age groups ( $</\ge70$  years), time since last SARS-CoV-2 infection (<6, 6-12, >12 months), time between primary course and first booster ( $</\ge12$  months), time between first and second booster ( $</\ge12$  months), and bivalent booster brand (Pfizer-BioNTech and Moderna).

*All-cause mortality (objective #3)* 

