In secondary cohorts of individuals aged  $\geq 18$  years with presumed immunocompromised conditions, we will evaluate the effectiveness of the bivalent boosters received as the  $\geq 4$ th dose. We will utilize the same analytical matched approach as in the main analysis described above. Dependent on the data distribution, time of VE assessment may be day 180 or day 365 since booster vaccination. Similarly, dependent on data availability, we will further subgroup bivalent booster recipients according to booster received as fourth, fifth, or  $\geq$ sixth dose, and we will endeavour to assess similar subgroups as in the main cohort subgroup analyses including waning VE analysis. The VE estimates will be indirectly compared with the VE estimates from the main cohort analysis while stressing the limitations of such indirect comparisons.

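### Objective 4: the target trial conditions on number of previous doses, but the matching that emulates it does not, so pairs may differ in prior doses and the VE may mix dose contrasts

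*Protocol*

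**What the plan says.** Section 9.7 (Immunocompromised) sets the scope: "we will evaluate the effectiveness of the bivalent boosters received as the" fourth or any later dose, in people aged 18 or over. The method is given by reference: "We will utilize the same analytical matched approach as in the main analysis described above". Dose number appears there only as a possible subgrouping of bivalent recipients (fourth, fifth, sixth or later), if the data allow.

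In the target-trial table of section 9.1, the target-trial column randomises 1:1, "for immunocompromised population, conditional on number of previous doses received". The emulation column beside it says "randomization is assumed conditional on matching (in a 1:1 ratio) on baseline covariates" and does not name dose count.

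The approach being reused is set out under Procedures and Statistical analysis in 9.7:
- Boosted people are "matched on the day of vaccination with individuals who have not yet received a fourth dose".
- Matching is on age, "calendar time of last mutual vaccine dose (i.e., third or fourth dose), and the propensity score (with a calliper width of 0.01").
- The score is "a propensity score including sex, region of residence, vaccination priority groups", comorbidities and previous infection.

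Section 9.3 (Covariates) makes one addition for objective 4: "we will also include subtype of immunocompromised condition (as categorized in the 6 levels in the table above").

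**The concern.** In the main cohort, equal dose history is supplied by eligibility. Section 9.2 excludes anyone whose fourth dose came before the country start date, so boosted versus unboosted is four doses against three, and between-booster comparisons are four against four. No dose-count key is needed.

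Objective 4 has no such safeguard. It admits boosters from the fourth dose upward, and its sixth qualifying condition brings in people with an early fourth dose or with five or more doses before the study. If matching does not then hold prior doses equal, the contrast within a pair may be the index booster plus one or more earlier doses, and the recency of the preceding dose is not controlled either.

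This matters for how the result will be used. Section 9.7 plans an indirect comparison with the main-cohort VE, and section 9.9 hopes the estimates will help in judging a schedule that involves more vaccinations. Dose number is central to both.

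**Working it through.** The Protocol states no sample size, event count, power or expected VE for objective 4, so there is no figure to reproduce. The check is mainly textual.

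**1. Is dose count anywhere in the emulation?**

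| Place | Number of previous doses |
|---|---|
| 9.1, target-trial column | Conditioned on, for this population |
| 9.1, emulation column | Not named; baseline covariates only |
| 9.3, covariates for objective 4 | Not named; subtype of condition added |
| 9.7, matching variables | Not named; age, month of third or fourth dose, propensity score |
| 9.7, propensity score content | Not named |
| 9.7, objective 4 text | Optional subgroup of recipients only |

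**2. Does the last mutual dose supply it?** The term suggests that a pair shares the dose preceding the index booster. But 9.3 and 9.7 spell it out only as the third dose (boosted versus unboosted) or the fourth (between boosters). For an index booster given as a fifth or sixth dose it has no definition. Carried over literally, a fifth-dose recipient would be matched on third-dose month to someone who has not had a fourth dose.

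**3. Does the subtype covariate supply it?** Only coarsely.
- Level 6 pools three routes: a booster within 90 days of the last dose, a fourth dose before roll-out, and five or more doses before the study period. The first can be met with three doses.
- Levels 1 to 5 are diagnoses and carry no dose information. By the footnote in 9.2, roll-out in Finland, Norway and Sweden began around February or March 2022, before the study period. Someone with a qualifying diagnosis and a fourth dose between those dates need not meet level 6, yet would receive a bivalent booster as a fifth dose.

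**4. Between boosters.** Nothing listed prevents fifth-dose BA.4-5 from being paired with fourth-dose BA.1.

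**5. Which way would unequal pairs push the VE?** An illustration in which every input is an assumption:
- V: true VE of the index booster at equal prior doses.
- s: share of pairs in which the recipient had one more prior dose than the comparator.
- r: residual protection from that extra dose.
- c: risk ratio, left after matching, for people given more doses because they are frailer.

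Apparent VE = 1 − (1 − V) × [(1 − s) + s(1 − r)c].

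With r = 0.3 and c = 1, (1 − r)c = 0.70:
- V = 60%: s = 0.3 gives 1 − 0.4 × 0.91 = 63.6%; s = 0.6 gives 1 − 0.4 × 0.82 = 67.2%.
- V = 40%: 1 − 0.6 × 0.91 = 45.4%; 1 − 0.6 × 0.82 = 50.8%.

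With r = 0.1 and c = 1.5, (1 − r)c = 1.35:
- V = 60%: s = 0.3 gives 1 − 0.4 × 1.105 = 55.8%; s = 0.6 gives 1 − 0.4 × 1.21 = 51.6%.
- V = 40%: 1 − 0.6 × 1.105 = 33.7%; 1 − 0.6 × 1.21 = 27.4%.

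The sign turns on whether (1 − r)c is below or above 1. The Protocol gives neither r nor c. These figures show that the direction is open; they do not estimate a bias.

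**The case against.** The best defence is that the principle is already stated. Section 9.1 conditions on number of previous doses, and the emulation column does not disclaim it. The third-or-fourth-dose wording was written for the main cohort, where the booster is always the fourth dose. Reusing the approach for later doses must mean reusing the method, not that text verbatim, and the last mutual dose then reads naturally as whatever dose both members share. Subtype level 6 carries some dose history. The objective is secondary and depends on the data, and exact match keys are often left to an analysis plan.

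Part of this stands. Same-dose matching may well be intended. A reader might infer that people with four or five doses can never serve as unboosted comparators, but that rests on applying main-cohort wording literally, and no section says it. Having one dose fewer than the recipient is, of course, the intended contrast when boosted are compared with unboosted; the problem is a gap of two or more.

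The gap nevertheless remains. The Protocol does not defer its matching set to another document. It enumerates the set, states what objective 4 adds, and omits the one variable that its own target trial requires.

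**Conclusion.** The point holds as an internal inconsistency that should be fixed. For objective 4 the emulation does not carry through the conditioning on number of previous doses, and as written it allows pairs with unequal prior doses. The VE can then mix contrasts such as four against three and five against three.

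A reader might infer that the VE will be overstated because earlier doses are credited to the index booster. The documents do not support a direction: extra doses also mark more severe immunocompromise, as the sixth qualifying condition itself recognises, and that pushes apparent VE down. Nor do they support a size. The share of unequal pairs is unknown, and the VE of about 66% to 68% quoted in section 7 comes from people aged 50 or older after a fourth dose, so it cannot stand in for the residual protection of an intermediate dose in this cohort.

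The conclusion rests on the matching and covariate lists being complete as printed. No primary objective that uses the main cohort's matching is affected, because eligibility there fixes the dose count.

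**What to change.** In sections 9.3 and 9.7, for objective 4:
- Match exactly on number of vaccine doses received before the index date.
- Define the unboosted reference as a person with that same number of doses and no further dose by the index date.
- For boosted versus unboosted, extend the last mutual vaccine dose to that same-numbered dose, in monthly bins.
- For between-booster comparisons, require the index booster to be the same dose number in both arms.
- Repeat the dose-count condition in the emulation column of the table in 9.1.

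A further rule barring any bivalent dose before the index date is a separate eligibility question and is not needed for this point.

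The cost is protocol wording, one extra match key from vaccination data already held, and somewhat fewer matched pairs. Because one set of R scripts runs in all four countries (section 9.6), the change is best made before those scripts are final.

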### 9.8 Supplementary analyses and quality control

Quality control will be conducted indirectly to evaluate the validity of our main analyses, by 1) making sure that the prevalence of the different schedules and the number of study endpoints match national surveillance dashboards and reports, 2) descriptive and analytical results cohere to our previous findings, and 3) using a Common Data Model (CDM), by which national register data are standardised to a common structure, format and terminology in order to allow the same statistical programming scripts to be used in each country. The use of a CDM with common statistical programming scripts will facilitate efficient use of resources and reproducibility of the statistical analyses. We will ensure the scientific quality of the work, by division of review tasks (including statistical code review) and responsibilities in a timely fashion and by adhering to the ENCePP Code of Conduct (see attachment). We will perform matching quality diagnostics to assess the control of matched parameters. For the 4 vs 3 dose comparisons, we will include a sensitivity analysis where starting follow after day 21/28 after the index date for the main comparison to further reduce the potential of transient healthy vaccinee effect around the time of vaccination as well as spill-over effect (that is, prior to the index date) given that some severe Covid-19 events may take longer time to develop. Lastly, in case data do not allow for 365-day effectiveness estimation (e.g., owing to heavy censoring of matched pairs), we will, similarly to the comparison analyses among immunocompromised, use an alternative shorter length of follow-up (e.g., day 180/270).

#### 9.9 Limitations of the research methods

The study has a number of limitations. First, the observational nature of the study hampers the possibility to fully exclude residual unmeasured confounding. A major concern would be presence of such unmeasured confounding factors that were unevenly distributed between compared matched

groups (i.e., not indirectly adjusted for by the set of included covariates, that is, proxies). We will include a range of pre-specified confounders and study a population representative of the general audience targeted for bivalent booster vaccinations. The precision of our exposure, Covid-19 vaccination, will rely on the registered vaccination within the registers and recorded time of administration. To the best of our knowledge, the assignment of the type of booster as the fourth dose was unselective during the study period (except for the initial prioritisation of older and vulnerable individuals during the first two weeks of study period in Denmark) and our study period should reflect a time of which fourth dose vaccination was offered to the general public.

For the outcomes of Covid-19 hospitalisation and death, our outcome definition will most likely also capture a small proportion of cases where the infection with SARS-CoV-2 only partly contributed to or coincided with the timing of hospitalisation, that is, hospitalisations or deaths where SARS-CoV-2 infection were not the sole cause. In addition, those acquiring SARS-CoV-2 infection (and who were hospitalised or died) without PCR test results we will not capture; we have no information on at-home antigen testing for SARS-CoV-2 infection. PCR testing has been advised as confirmatory to antigen testing and recommended for individuals at risk of severe Covid-19. Any of such outcome misclassification would most likely tend to bring the estimates toward a null effect.

These abovementioned potential limitations are mitigated by our utilization of an active comparative design as opposed to comparisons with unvaccinated. In the 4 vs 3 comparisons (i.e., fourth dose boosted vs nonboosted), the follow-up among those who have not received a fourth dose is contributed from individuals who have yet to receive a fourth dose and individuals who will never receive a fourth dose. In the more immediate time-periods following the index date, the comparison is dominated by the former group while closer to day 365 of follow-up the comparison is dominated by the latter group. Individuals who never receive a fourth dose are more likely to be different from those who elect to get booster vaccination and this can introduce e.g., healthy vaccinee bias if these differences are not accounted for by the included covariates.

Our statistical precision will rely on the overlap of covariate distributions between comparisons (affecting the final matched cohort sizes). As a consequence, the possibilities for direct head-to-head comparison between bivalent and monovalent boosters as a fourth dose will most likely be limited due to the less overlap of calendar periods of use and the need for stringent control hereof (due to otherwise potential confounding by e.g., differences in waning of third dose, background population infection rates, and circulating variants).

Both vaccination status and SARS-CoV-2 variants of predominance are strongly correlated with calendar time. This limits possibilities for directly comparing effectiveness estimates obtained during different variants predominance periods (background transmission rates and population characteristics most likely differ) as well as evaluating longer-term follow-up effectiveness in relation to only one SARS-CoV-2 variant. As such, the analyses will instead reflect evaluations of the initiated Covid-19 vaccination strategies at that given time.

We aim to perform a panel of different subgroup and secondary analyses to extend current knowledge of the impact of timing of vaccination in relation to both previous SARS-CoV-2 infection and vaccination schedules received. However, we do not aim to address hybrid immunity of vaccination followed by a subsequent infection on future Covid-19 risk, given that such analysis with use of observational data would be hampered by collider bias.(40)

As we take confounders into account by matching to emulate a target trial that provides causal inference of the effectiveness of bivalent booster vaccination, our estimands represent the average treatment effect among treated, and, thus, results from the individual matched comparisons should primarily be interpreted separately. Consequently, an indirect comparison of for example VE among immunocompromised with VE in the general (immunocompetent) population is not ideal. Research questions such as "is the special vaccination schedule for immunocompromised, with shorter interval between doses and more vaccinations necessary?" and "does the special vaccination schedule for immunocompromised have the desired effect on VE?" are not straightforward and cannot be directly answered by use of our observational data. This would necessitate a comparison group of immunocompromised following the vaccination schedules of the general population and no overlap of such treatment strategies (i.e., vaccination programmes) exists within our real-world data due to the distinct vaccination recommendations set out for individuals with immunocompromised conditions by the national health authorities. However, if the size of the data allows, we will be able provide VE as well as waning effectiveness estimates among immunocompromised which can assist the evaluation of such study questions to some extent.

Given the broad inclusion within each Nordic country, our results will likely have a high degree of generalisability to other similar populations. However, our assessment of the comparative effectiveness of bivalent mRNA-booster vaccines given as a fourth dose against severe Covid-19 outcomes may only indirectly support any evaluation of the effectiveness of these vaccines within other Covid-19 vaccination schedule scenarios. Our findings may similarly not directly generalize to certain subpopulations not individually studied or to populations with a demographically different

composition. Such subpopulations include for example the general population younger than 50 years old or other specific clinical subgroups that were not studied.

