#### 12. PLANS FOR DISSEMINATING AND COMMUNICATING STUDY RESULTS

Main results expected in the final study report:

- Tables of baseline characteristics before and after matching
- Figures of matching quality diagnostics
- Figures of cumulative incidences of severe Covid-19 outcomes until day 365 since day of fourth dose vaccination
- Tables of effectiveness estimates for all and by subgroups of the main study cohort
- Figures of waning VE for main study cohort (and immunocompromised study cohort if possible)
- Tables of association estimates for all and by subgroups of the all-cause mortality cohort
- Tables of effectiveness estimates for all and by subgroups of the immunocompromised study cohort

We anticipate multiple manuscripts, and findings will be reported to the general public by institutional press releases upon acceptance in academic peer-review journals or upon uploading to pre-print server (if decided relevant to do so).

We will adhere to the STROBE and ENCEPP guidelines when reporting results and drafting the manuscript(s).

Example of tables of main results:

	Country-combined measures of association (95% CI) at day 3 of follow-up				
	COVID-19 hospitalization COVID-19 deat			19 death	
	RD	CVE	RD	CVE	
4- vs 3-dose schedule analysis					
Fourth dose bivalent BA.1 boosted vs nonboosted					
All	XX (XX to XX)	XX (XX to XX)	XX (XX to XX)	XX (XX to XX)	
Strata					
Male	XX (XX to XX)	XX (XX to XX)	XX (XX to XX)	XX (XX to XX)	
Female	XX (XX to XX)	XX (XX to XX)	XX (XX to XX)	XX (XX to XX)	
<70 years					
≥70 years					
<6 months since last SARS-CoV-2 infection					
6-12 months since last SARS-CoV-2 infection					
>12 months since last SARS-CoV-2 infection					
<1 year between primary course and booster					
≥1 year between primary course and booster					
<1 year between first and second booster					
≥1 year between first and second booster					
BNT162b2 as fourth dose					
mRNA-1273 as fourth dose					
Fourth dose bivalent BA.4-5 boosted vs nonboosted					
All					
Strata					
Etc.					
Fourth dose monovalent (original) boosted vs nonboosted					
(additional comparison)					
All					
Strata					
Etc.					
4- vs 4-dose schedule analysis					
Bivalent BA.4-5 vs bivalent BA.1 boosted					
All					
Strata					
Etc.					
Bivalent BA.4-5 vs monovalent (OG) boosted (additional					
comparison)					
All					
Strata					
Etc.					
Bivalent BA.1 vs monovalent (OG) boosted (additional					
comparison)					
All					
Strata					
Etc.					

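### The protocol sets out to learn the impact of vaccination timing but specifies only VEs within timing strata, with no contrast between them, and leaves the timing cut-points both fixed and open

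*Protocol*

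**What the plan says.** **Aim.** Secondary objectives 6 and 7 (section 8) ask for day-365 VE according to time since a previous infection and according to between-dose intervals. Section 9.9 states what the subgroup work is for: "to extend current knowledge of the impact of timing of vaccination in relation to both previous SARS-CoV-2 infection and vaccination schedules received".

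**Analysis.** Section 9.7, Statistical analysis, says: "Subgroup analyses will be conducted according to sex, age groups", and goes on to "time since last SARS-CoV-2 infection (<6, 6-12, >12 months"), two between-dose intervals cut at 12 months, and "bivalent booster brand (Pfizer-BioNTech and Moderna"). VE is 1 minus the risk ratio, with a delta-method 95% CI, pooled by random-effects meta-analysis. The same section does specify a formal contrast for waning: a meta-regression giving a ratio of VEs per three-month interval. It names no contrast between subgroup strata.

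**Reporting.** Section 12 promises "Tables of effectiveness estimates for all and by subgroups of the main study cohort". Its example table has a row per stratum, such as "<1 year between primary course and booster" and "<1 year between first and second booster", with risk difference and comparative VE for hospitalisation and for death.

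**Cut-points.** The covariate table in section 9.3 gives three levels for time since infection and two for each dose interval, and sections 9.7 and 12 repeat them. The text above that covariate table says of the same three variables: "we will assess the data distribution to help find the optimal categorization of the variables".

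**The concern.** The impact of timing is a difference in VE between people vaccinated sooner and later after an infection or an earlier dose. A list of stratum VEs does not estimate that difference or its uncertainty. A reader of the planned tables would have to judge by eye, and the easy shortcut is to note that one stratum's CI excludes zero while another's does not. When strata differ in size, that shortcut often suggests effect modification where there is none.

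The cut-points add to this. They are stated in three places, yet section 9.3 leaves them open to re-selection, without saying what optimal means or that the choice precedes any look at outcomes by stratum. The variables affected are the ones that carry the timing question.

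**Working it through.** The protocol gives no subgroup power, event count or error rate, so there is no stated figure to reproduce.

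**1. Number of stratum VEs.** The levels in sections 9.7 and 12 are sex 2, age 2, time since infection 3, primary-to-booster interval 2, first-to-second booster interval 2, brand 2. Total 2+2+3+2+2+2 = 13, of which timing accounts for 3+2+2 = 7. There are two outcomes. The example table has six comparisons, five of them abbreviated.

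| Comparisons counted | Stratum VEs | Timing only |
|---|---|---|
| All six | 13×6×2 = 156 | 7×6×2 = 84 |
| Five involving a bivalent booster | 13×5×2 = 130 | 7×5×2 = 70 |
| Three not marked as additional | 13×3×2 = 78 | 7×3×2 = 42 |

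**2. Discordant significance when true VE is equal.** For a stratum with E events in two arms of equal size and risk ratio RR:

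- e0 = E/(1+RR) and e1 = E − e0
- SE(log RR) = √(1/e0 + 1/e1)
- power p = Φ(|log RR|/SE − 1.96), ignoring the negligible opposite tail
- for two independent strata, P(exactly one CI excludes zero) = p1(1−p2) + p2(1−p1)

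Worked case, VE 30% (RR 0.70), 500 events split 100/400:

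- Small stratum: e0 = 58.8, e1 = 41.2, SE = 0.203, |log RR|/SE = 0.357/0.203 = 1.76, p = 0.42.
- Large stratum: e0 = 235.3, e1 = 164.7, SE = 0.102, ratio 3.51, p = 0.94.
- Discordance = 0.42×0.06 + 0.94×0.58 = 0.57.

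| True VE in both strata | Events | Split | Powers | Discordance |
|---|---|---|---|---|
| 30% | 500 | 50/50 | 0.79, 0.79 | 33% |
| 30% | 500 | 20/80 | 0.42, 0.94 | 57% |
| 30% | 500 | 10/90 | 0.24, 0.96 | 74% |
| 20% | 1,000 | 20/80 | 0.35, 0.88 | 62% |
| 67.8% | 500 | 50/50 | 1.00, 1.00 | about 0% |
| 67.8% | 500 | 20/80 | 0.998, 1.00 | 0.2% |
| 67.8% | 500 | 10/90 | 0.93, 1.00 | 7% |
| 67.8% | 100 | 20/80 | 0.59, 0.99 | 42% |
| 0% | any | any | 0.05, 0.05 | 9.5% |

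The 67.8% is the earlier Nordic study's BA.4-5 VE against hospitalisation (section 7). The other VEs, and all event totals and splits, are assumptions.

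**3. What a direct contrast gives.** The log ratio of risk ratios is log RR1 − log RR2, with SE = √(SE1² + SE2²). In the worked case this is √(0.203² + 0.102²) = 0.227. If the true ratio is 1, a typical 95% CI runs from exp(−1.96×0.227) = 0.64 to exp(1.96×0.227) = 1.56. The reader then sees how little the data say about a difference.

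**4. What the contrast does not remove.** One heterogeneity contrast per factor (2 df for infection, 1 df otherwise) gives 6 per comparison and outcome: 72, 60 or 36 in all. At 5% each with no effect modification, 3.6, 3.0 or 1.8 false positives are expected. The chance of at least one, if independent, is 1 − 0.95^72 = 97.5%, 1 − 0.95^60 = 95.4% or 1 − 0.95^36 = 84.2%.

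**The case against.** The best defence is that objectives 5 to 8 are secondary, ask only for VE estimates, and get them. No significance rule is attached to the subgroups. Section 9.5 warns of reduced subgroup power. Section 9.9 says that results from individual matched comparisons are mainly to be read separately, and that calendar time and variant limit comparisons of effectiveness. Anyone can form the ratio of risk ratios from the reported CIs.

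Much of this stands. A reader might infer that chance differences will be reported as effect modification. The documents support only a risk of that, since they set no such rule. A reader might also count the missing exploratory label and multiplicity adjustment as errors, but these commonly sit in an SAP, which is not shown. The high discordance figures depend on moderate VE or few events and nearly vanish at the protocol's own 67.8% with 500 events.

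What does not stand is the claim that estimation within strata is enough. Section 9.9 states a between-stratum aim, and section 9.7 writes out a contrast for waning but none for timing. The advice on separate interpretation concerns separate matched comparisons and does not expressly cover strata. If it did, it would conflict with the timing aim.

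On cut-points, the text refers to the distribution of the covariates and names no outcome data, so it does not show outcome-driven selection. The conflict with the stated levels remains.

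**Conclusion.** The point holds for objectives 6 and 7. The protocol states a timing question, specifies no estimate that answers it, and gives the timing categories as both fixed and open.

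The size is uneven. For hospitalisation in large 4-vs-3 strata, discordance under equal VE is about 0-7% at VE 67.8% and 500 events. That VE comes from follow-up to day 90 (section 9.5), so the day-365 value may differ. Where VE is moderate or events are few, as may happen in 4-vs-4 comparisons, for deaths or in sparse strata, discordance can reach 40% or more: 57% at VE 30% with 500 events split 20/80, or 42% at VE 67.8% with 100 events split 20/80. These figures assume independent strata and arms of equal size.

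Two wider readings are not supported. The figure of 156 is the example table with every abbreviated row filled in. Objectives 5 to 8 concern a bivalent booster, which gives 130, or 78 without the comparisons marked as additional. And the timing aim does not extend to sex, age or brand. This is a worthwhile, inexpensive improvement; the stratum VEs themselves remain valid to report.

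**What to change.** In section 9.7, for the three timing factors and preferably the other subgroup factors:

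1. Compute within each country the ratio of risk ratios between strata (2 df for the three infection levels). The variance is the sum of the stratum variances, approximately so where re-entering individuals contribute to both strata.
2. Pool it with the same random-effects meta-analysis and report it with a 95% CI beside the stratum VEs in section 12.
3. Base statements about timing on this contrast and call them exploratory, because up to 72 contrasts remain.
4. State that dose-interval contrasts may still be confounded by calendar time and circulating variant, as section 9.9 already recognises for comparisons across periods.

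In section 9.3, reconcile the re-categorisation sentence with the stated levels: either use the stated cut-points, or allow changes only from covariate distributions and before outcome data by stratum are seen. The second option keeps a way out of sparse strata.

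The cost is one extra column, built from estimates and variances that the countries already return for pooling, plus a few sentences. No individual-level data cross borders. The downside is that fewer subgroup differences can be claimed.
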